Virological response rates and non-response categories will be displayed for patients who completed treatment with ABBVIE regimen, as well.

SVR12 (Exploratory Analyses)

Univariate logistic regression methods will be used to investigate the impact of various explanatory covariates (patient and disease characteristics) at baseline on SVR12.

These analyses will be of exploratory nature, data driven, and will be performed for CP population.

The variables to be considered are as follows:

- Key demographic information
 - Age (continuous)

- Gender (Female [reference], Male)
 - Race/ethnic origin (White/Caucasian [reference], Black, Asian/Oriental, Other [all other races]); at least two categories with at least 10% of the patients each have to exists, so that this variable will be considered
 - Weight (continuous)
 - BMI (continuous)
 - IL28B, rs12979860 (CC [reference], CT or TT); patients with unknown genotype are excluded from the respective analyses.
- CHC disease characteristics
 - Years since diagnosis (continuous)
 - Mode of CHC infection (Drug use [reference], Other [all other answers excluding unknown], unknown);
 - Most recent stage of liver fibrosis (No cirrhosis/Transition to cirrhosis [reference], Cirrhosis; for definition see 4.2.6.2);
- HCV RNA level at baseline (\log_{10} IU/mL)
- HCV genotype(G1a*, G1b, G4; for definition see section 4.2.6.2)
- Type of treating institute (Private Practice / Private Hospital, Academic / University Hospital, General Hospital, Other)
- Co-infections (every patient not reporting the respective co-infection is considered as not having the respective co-infection)
 - HIV(No [reference], Yes)
 - HBV(No [reference], Yes)
- Liver and/or CHC related co-morbidities (every patient not reporting the respective co-morbidity is considered as not having the respective co-morbidity)
 - Liver transplantation (No [reference], Yes)
 - Steatosis (non-alcoholic) (No [reference], Yes)
 - Decompensated liver disease (No [reference], Yes)
- Other co-morbidities (every patient not reporting the respective co-morbidity is considered as not having the respective co-morbidity)
 - Depression (No [reference], Yes)
 - Diabetes mellitus (No [reference], Type 1/Type 2)
 - Hypertension (No [reference], Yes)
 - Immunologically mediated disease (No [reference], Yes)

- Hypothyroidism (No [reference], Yes)
- Alcohol use (None [reference], Yes –occasional, Yes –regular, Exdrinker)

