- Key clinical chemistry and hematology laboratory variables at baseline
 - ALT ratio (continuous, see 4.2.6.5)
 - AST ratio (continuous, see 4.2.6.5)
 - Platelets [$10^9/L$] (continuous)
- Prior treatment status (HCV treatment naïve [reference], HCV treatment experienced)
- RBV vs no RBV
- Planned treatment duration 12 wks vs 24 weeks

The categories pre-specified above could be modified in the analyses if this is supported by the data (e.g. categories could be combined, if their impact on SVR12 is similar). Furthermore, continuous variables can be replaced by categorical variables.

Adherence

Adherence will be displayed for the CP by genotype and cirrhosis status and for the SP by treatment regimen and cirrhosis status. Summary statistics (n, mean, median, standard deviation [SD], and range) will be generated for continuous variable. Numbers and percentages of patients will be presented for categorical variables.

- Adherence to ABBVIE regimen (% of target dose [adherence=cumulated number of pills taken /(initial prescribed number of pills x planned duration)])
 - >105%
 - >95%-<=105%
 - >80%-<=95%
 - >50%-<=80%
 - <=50%
- Adherence to ribavirin (% of target dose [adherence=cumulated dose taken /(initial prescribed dose x planned duration)])
 - >105%
 - >95%-<=105%
 - >80%-<=95%
 - >50%-<=80%
 - <=50%

- Percentage of actual treatment duration in relation to the target duration of ABBVIE regimen taken
- Deviating duration of ABBVIE regimen
 - Early discontinuation (actual duration is shortened for more than 7 days)
 - Not deviated
 - Exceedance (actual duration is prolonged for more than 7 days)
- Method used to document adherence (Interview, Diary)
- Percentage of actual days with treatment with RBV in relation to the planned duration
- Ribavirin earlier discontinued than ABBVIE regimen
- Initial dose of Ribavirin
 - 1000 mg/day
 - 1200 mg/day
 - XXX
- Cumulative dose of Ribavirin (g)
- Dose modifications/termination of RBV [in patients taking RBV, for a patient more than one dose modification and its main reason could be reported, but for each single reason the patient is counted only once] (Total number of patients with lower dose than highest previous dose [including patients who stopped the treatment earlier], Anemia, Nausea/Vomiting, Rash, Other [including patients who discontinued ABBVIE regimen earlier, but did not stop the RBV treatment before the ABBVIE regimen])

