In addition to the summary statistics of the adherence variables, logistic regression analyses will be performed for the following adherence variables: "adherence to ABBVIE regimen" in all patients of the CP, "adherence to ribavirin" in all patients of the CP taking RBV, each categorized as follows: >=95%, >80%-<=95%, <=80% to investigate the additional impact of overall treatment adherence on SVR12. The categories may be changed if they are sparsely filled. Adherence will be included as mandatory covariate in addition to the baseline explanatory variables already mentioned above. Also the same methods will be applied as described above.

An overview of Tables is given in Table 7.

Table 7 Overview of Outputs for Primary and Secondary Effectiveness Analysis

Output Title	Output Short Name	Analysis Population
Virological Response Rates by Genotype and Cirrhosis Status – CP/CPSFU - <country>	tvr_<c>_gc_cp	Core population/ Core population with sufficient follow-up data
Virological Response Rates by Genotype and Cirrhosis Status in Patients who Completed ABBVIE Regimen – CP/CPSFU - <country>	tvr_<c>_gc_cp_ARC	Core population/ Core population with sufficient follow-up data: patients who completed ABBVIE regimen
Virological Response Rates - NCP - <country>	tvr_<c>_ncp	Non-core population
Relapse Rates by Genotype and Cirrhosis Status – CP - <country>	trr_<c>_gc_cp	Core population
Viral Breakthrough by Genotype and Cirrhosis Status – CP - <country>	tvb_<c>_gc_cp	Core population
Non-Response Rates by Genotype and Cirrhosis Status – CP - <country>	tnrr_<c>_gc_cp	Core population
Non-Response Rates by Genotype and Cirrhosis Status in Patients who Completed ABBVIE Regimen – CP - <country>	tnrr_<c>_gc_cp_ARC	Core population: patients who completed ABBVIE regimen
Impact of Patient and Disease Characteristics on SVR12 – CP - <country>	tis_<c>_cp	Core population
Adherence by Genotype and Cirrhosis Status - CP - <country>	tah_<c>_gc_cp	Core population
Adherence by Treatment Regimen and Cirrhosis Status - SP - <country>	tah_<c>_tc_sp	Safety population
Impact of Adherence to ABBVIE Regimen on SVR12 – CP - <country>	tiaa_<c>_cp	Core population
Impact of Adherence to Ribavirin on SVR12 in patients taking RBV – CP - <country>	tiar_<c>_cp_RBV	Core population: patients taking RBV

The layouts of the tables mentioned above are provided in Part II of the SAP (Table Shells).

4.2.7.2.2 *Quality of life*

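### The ribavirin-adherence analysis of SVR12 does not account for DAA adherence, so SVR12 lost through missed DAAs can appear as an effect of ribavirin adherence

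*SAP*

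**What the plan says.** SAP 4.2.7.2.1 plans two logistic analyses of adherence against SVR12. One takes adherence to the DAAs in the whole CP. The other takes adherence to RBV "in all patients of the CP taking RBV, each categorized as follows: >=95%, >80%-<=95%, <=80"%. Their stated purpose is "to investigate the additional impact of overall treatment adherence on SVR12".

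Table 7 gives each its own output: "Impact of Adherence to ABBVIE Regimen on SVR12" (tiaa) and "Impact of Adherence to Ribavirin on SVR12 in patients taking RBV" (tiar).

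For the model content the SAP states: "Adherence will be included as mandatory covariate in addition to the baseline explanatory variables already mentioned above". The list it refers back to is introduced as the "impact of various explanatory covariates (patient and disease characteristics) at baseline on SVR12". It holds patient and disease characteristics, RBV yes/no and planned duration. It has no term for DAA adherence, actual duration or early discontinuation.

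DAA adherence is defined as "cumulated number of pills taken /(initial prescribed number of pills x planned duration"), and RBV adherence as "cumulated dose taken /(initial prescribed dose x planned duration").

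Protocol 9.7.3.3 adds only that logistic regression will also be used for the impact of adherence on SVR12.

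**The concern.** The two measures are built the same way and the drugs are taken together. A patient who stops the whole regimen early, or who skips whole days, scores low on both. A patient who takes every DAA tablet and only reduces or stops RBV scores low on RBV alone. The SAP foresees both: its adherence summaries record RBV stopped earlier than the DAAs, and its RBV-termination item counts patients who ended both together. In tiar these two kinds of patient share one class, and nothing in the model separates them.

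This is confounding by the co-administered drugs. It is a different matter from the choice of denominator, and another denominator would not remove it for patients who skip all tablets on the same days.

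The influence of adherence on outcome is a stated secondary objective, and tiar is the only analysis of RBV adherence against SVR12. A reader could take it as evidence about RBV intake when it reflects DAA intake. The SAP's handling of missing data strengthens the shared path: a CP patient with no usable HCV RNA value after flanking and backward imputation counts as a failure, and that can include early stoppers who do not return.

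**Working it through.** The plan gives no figure for these models, so there is none to reproduce. The checks below use the SAP's definitions and stated assumptions.

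**1. Do both measures fall together?** Take a 12-week plan (84 days), with RBV planned for the same period and all tablets stopped on one day.
- Stop after day 42: 42/84 = 50.0% on both measures.
- Stop after day 67: 67/84 = 79.8% on both measures.

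Either patient is in the <=80% class for DAAs and for RBV.

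**2. What does tiar show when RBV adherence has no effect?** Assumptions:
- SVR12 is 97% in everyone who completes the DAAs, whatever the RBV intake. This is the upper end of the 95-97% in Protocol 7.1, Table 1, for treatment-naive genotype 1a with RBV.
- A share *s* of RBV takers stops everything early, with SVR12 *p*.
- A share *r* falls to <=80% RBV with full DAA intake.

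The documents do not give *s*, *p* or *r*.

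SVR12 in the low RBV class = (*s* × *p* + *r* × 0.97)/(*s* + *r*). The high class has 0.97, with odds 0.97/0.03 = 32.33.

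| *s* | *p* | *r* | Low-class SVR12 | Odds | Odds ratio, low vs high |
|---|---|---|---|---|---|
| 5% | 60% | 10% | (0.030 + 0.0970)/0.15 = 84.7% | 5.52 | 0.17 |
| 10% | 30% | 10% | (0.030 + 0.0970)/0.20 = 63.5% | 1.74 | 0.05 |
| 3% | 60% | 25% | (0.018 + 0.2425)/0.28 = 93.0% | 13.36 | 0.41 |

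The last two rows are the extremes over *s* = 3, 5, 10%, *p* = 30, 60% and *r* = 10, 25%. A second grid (SVR12 95-97% with high and 50-80% with low DAA adherence, *s* 3-10%, *r* 0-20%) gives 0.03 to 0.70. The true odds ratio is 1.0 throughout. Under this set-up the result stays below 1 unless no RBV taker has low DAA adherence or DAA adherence has no effect on SVR12.

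**3. How many failures will there be?** SAP 3.2 expects 50-55 patients. The number on RBV is not given; 20 to 40 is assumed. Expected failures run from 20 × 0.03 = 0.6 to 40 × 0.05 = 2.0.

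**4. Can an odds ratio be estimated?** Simulation with 20 to 40 RBV takers and adherence as low/high at 80%. The figure is the share of runs with no finite odds ratio.

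| Analysis | Scenario | Not estimable |
|---|---|---|
| RBV term only, as planned | First row of the table in step 2 | about 61-87% |
| RBV term only, as planned | Whole grid of step 2 | about 41-91% |
| Restricted to full DAA intake | First row of the table in step 2 | about 93-98% |
| Restricted to full DAA intake | Whole grid of step 2 | about 85-98% |
| RBV and DAA terms together | 5-10% stop, 15% reduce RBV only, SVR12 95% vs 50% or 97% vs 70% | about 85-99.7% |

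After restriction only about 0.5 to 1.2 failures are expected. For example, with 5% stoppers among 40 patients: 40 × 0.95 × 0.03 = 1.14.

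**The case against.** The strongest case against is that this asks a drug-specific causal question the SAP does not pose. The stated aim is overall treatment adherence, the analyses are declared exploratory and data driven, and Protocol 9.9 already names uncontrolled confounding as a limitation. The reader will also have tiaa beside tiar, descriptive RBV items (early RBV stop, days, cumulative dose, reasons for reduction), and response tables limited to patients who completed the regimen. The table shells in SAP Part II are not available here and might carry a footnote. The sentence on the mandatory covariate does not expressly exclude a second adherence term.

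Part of this stands. The point concerns how a secondary table is read, and it is minor. But none of the tables listed in the SAP crosses SVR12 with RBV class within DAA class. Two separately named variables, two populations and two outputs make one adherence term per model the natural reading. A table whose title speaks of the impact of ribavirin adherence invites the drug-specific reading.

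The second objection is that the large odds ratios are population values which the study will rarely display, because failures are so few. This stands in full, and it rules out the more ambitious remedies: a model with both terms, or restriction to DAA adherence >95%, would usually give no finite odds ratio.

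A reader might also infer that tiar is the only RBV analysis in the plan. It is not: RBV versus no RBV is itself a covariate for SVR12.

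**Conclusion.** The concern holds as an interpretive defect in one exploratory secondary output. As described in SAP 4.2.7.2.1, tiar cannot separate RBV intake from DAA intake, and whole-regimen stopping pushes its result towards an apparent harm of low RBV adherence. In the illustration that is 84.7% against 97% (odds ratio 0.17), with a range of 0.05 to 0.41 over the main grid. The stopping and reduction rates, the SVR12 of stoppers and the number of RBV takers are all assumptions. The direction does not depend on their exact values.

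Three stronger readings are not supported. The primary SVR12 estimate is not affected. The documents do not show that an odds ratio near 0.17 will be reported: with about 0.6 to 2 expected failures it will often not be estimable, and one patient who stopped everything could supply the whole apparent effect. Nor does the illustration say that RBV adherence is unimportant; it assumes no RBV effect only to show what the analysis would then report.

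**What to change.** In SAP 4.2.7.2.1 and output tiar:
- Add a cross-table of SVR12 n/N by RBV-adherence class, shown separately for DAA adherence >95% and <=95%, in CP patients taking RBV.
- Label any RBV-adherence odds ratio as not adjusted for DAA adherence and not separating RBV intake from DAA intake.

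The cost is a sentence of SAP text and one small table from variables already derived. Its cells will be sparse, and it will not yield an adjusted estimate. It will show whether the failures in the low RBV class also had low DAA intake.

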4.2.7.2.3 Treatment related health care resource utilization until EoT

Resource utilization within the four weeks prior to the start of the ABBVIE regimen and until EoT (since baseline) will be displayed for CP by genotype and cirrhosis status and for SP by treatment regimen and cirrhosis status.

Information on outpatient consultations (i.e. number of outpatient consultations [defined as sum of all visits] - continuous and categorized as 0, 1-3, 4-6, >=7), and hospitalizations (.i.e. number of hospitalization periods [defined as sum of all visits] - continuous and categorized as 0, 1, 2-3, >=4, duration of hospitalization [days; defined as sum of all visits] - continuous and categorized as 0, 1-7, 8-14, >=15, and number of technical interventions [defined as sum of all visits] - continuous and categorized as 0, 1-3, 4-6, >=7) within the four weeks prior to the start of the ABBVIE regimen and until EoT (since baseline) will be summarized.

Outpatient consultations

Outpatient consultations within the four weeks prior to the start of the ABBVIE regimen and until EoT (since baseline) will be summarized in a table. The following variables will be displayed:

- Interventions performed (patient is counted at most once per intervention):
 - Lab test panels ordered (panel is any of a set of lab tests ordered at the same time)
 - Blood transfusion
 - Administration of erythropoietic growth factor
 - Administration of G-CSF
 - Invasive diagnostic intervention
- Symptoms treated (patient is counted at most once per symptom):
 - Abdominal distension
 - Abdominal pain

- Alopecia
- Anemia
- Anxiety
- Change in thyroid function
- Changes in bowel habits
- Dark brown urine
- Depression / mood disorder
- Disturbed sleep
- Edema
- Fatigue
- Flu-like symptoms
- Impaired sense of taste
- Increase in blood sugar level
- Itching
- Jaundice
- Leukopenia
- Loss of appetite
- Nausea
- Neutropenia
- Rash
- Thrombocytopenia
- Weight gain
- Weight loss
- Other

Hospitalization

Hospitalization within the four weeks prior to the start of the ABBVIE regimen and until EoT (since baseline) will be summarized, i.e:

- Interventions performed (patient is counted at most once per intervention):
 - Lab test panels ordered (panel is any of a set of lab tests ordered at the same time)
 - Blood transfusion
 - Administration of erythropoietic growth factor
 - Administration of G-CSF
 - Invasive diagnostic intervention
- Symptoms treated (patient is counted at most once per symptom):
 - Abdominal distension
 - Abdominal pain
 - Alopecia
 - Anemia
 - Anxiety
 - Change in thyroid function
 - Changes in bowel habits
 - Dark brown urine
 - Depression / mood disorder
 - Disturbed sleep
 - Edema
 - Fatigue

- Flu-like symptoms
- Impaired sense of taste
- Increase in blood sugar level
- Itching
- Jaundice
- Leukopenia
- Loss of appetite
- Nausea
- Neutropenia
- Rash
- Thrombocytopenia
- Weight gain
- Weight loss
- Other

Table 8 Overview of Outputs for Secondary Variables

Output Title	Output Short Name	Analysis Population
EQ-5D-5L by Treatment Regimen and Cirrhosis Status - CP - <country>	teq_<c>_tc_cp	Core population
WPAI by Treatment Regimen and Cirrhosis Status - CP - <country>	twp_<c>_tc_cp	Core population
Outpatient Consultations and Hospitalization Until EoT by Genotype and Cirrhosis Status - CP - <country>	toh_<c>_gc_cp	Core population
Outpatient Consultation Until EoT by Genotype and Cirrhosis Status - CP - <country>	toc_<c>_gc_cp	Core population
Outpatient Consultations and Hospitalization Until EoT by Treatment Regimen and Cirrhosis Status - SP - <country>	toh_<c>_tc_sp	Safety population
Outpatient Consultation Until EoT by Treatment Regimen and Cirrhosis Status - SP - <country>	toc_<c>_tc_sp	Safety population
Hospitalization Until EoT by Genotype and Cirrhosis Status - CP - <country>	thz_<c>_gc_cp	Core population
Hospitalization Until EoT by Treatment Regimen and Cirrhosis Status - SP - <country>	thz_<c>_tc_sp	Safety population

The layouts of the tables mentioned above are provided in Part II of the SAP (Table Shells).

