### **9.4.1.1 Inclusion Documentation**

Inclusion:

Patients will be included only after the physician and the patient have decided to treat chronic HCV with paritaprevir/r and ombitasvir +/- dasabuvir +/- ribavirine. To guarantee independence of prescription choice of the HCP, a nurse practitioner will check if a newly prescribed patient might be eligible for the study and if so, may inform the patient about participation in the observational study.

Patients can be enrolled in the PMOS during the first 4 weeks of treatment, enabling the nurse practitioner to search eligible newly prescribed patients also from medical records.

After the patient has been found eligible and after the informed consent has been signed, the following will be documented if available:

- Demographic information
  - Interleukin 28B (IL28B) genotypes
- CHC disease characteristics
  - Year of diagnosis and mode of infection
  - Stage of liver fibrosis/cirrhosis (Annex 4)
- CHC treatment history
  - Naïve or experienced
  - If experienced, most recent prior therapy and outcome
- Relevant medical history, co-morbidities and co-infections
- Concomitant medication, see 9.4.1.5
- ABBVIE REGIMEN ± RBV

- Laboratory data

Key clinical chemistry	Remarks
▪ ALT (alanine-aminotransferase)	including upper limit of normal (ULN),
▪ AST (aspartate-aminotransferase)	including ULN, AST to platelet ratio index (APRI) and Fibrosis-4 Score/Index (FIB-4)* will be calculated
▪ γ-GT (gamma-glutamyltransferase)	
▪ Total bilirubin	
▪ Albumin	
▪ Creatinine	creatinine clearance # will be calculated
▪ AFP	
Key hematology	
▪ Hb (Hemoglobin)	
▪ Platelets	
▪ Prothrombin time	or international normalized ratio (INR)
Virology	
▪ HCV genotype and subtype	
▪ HCV RNA	quantitative/ qualitative HCV RNA by polymerase chain reaction (PCR) test, see 9.4.1.4
HIV-infected patients only	
▪ CD 4 count (cluster of differentiation 4)	most recent assessment
▪ HIV RNA	in copies/mL

\*derived from patient's age, ALT, AST and platelets

#by Cockcroft-Gault-Formula based on creatinine, gender, age and weight

- Patient questionnaires, see Table 2 and 9.4.1.6
- Treatment related health care resource utilization

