## Annex 1. Healthcare Resource Utilization Questionnaire

### Visits:

#### Baseline

On treatment - Early treatment (if applicable),

On treatment - Week 12 (only for patients receiving 24 weeks of therapy),

End of treatment

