#### Baseline:

Outpatient Consultation(s) - Resource Utilization (in the 4 weeks prior to starting the ABBVIE REGIMEN)

Outpatient consultation(s) in the 4 weeks prior to starting the ABBVIE REGIMEN:

- 0 (no outpatient consultation)
- 1
- 2
- 3
- 4

Please document for each outpatient consultation in the 4 weeks prior to starting the ABBVIE REGIMEN the technical interventions performed and the symptoms treated:

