**Outpatient Consultation(s) - Resource Utilization (since last visit)****Outpatient consultation(s) since last visit:**

*Please document for each outpatient consultation since last visit the technical interventions performed and the symptoms treated.*

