Quality of life will be analyzed for CP by cirrhosis status (cirrhosis vs transition to cirrhosis/no cirrhosis) and treatment regimen (2DAA w/o RBV, 2DAA + RBV, 3DAA w/o RBV and 3DAA + RBV).

Assessment of general quality of life - EQ-5D-5L

The EQ-5D-5L is a health state utility instrument that evaluates preference for health status (utility). The 5 items in the EQ-5D-5L comprise 5 dimensions (mobility, self-care, usual activities, pain/discomfort, and anxiety/depression) each of which are rated on 5 levels of severity (1: indicating no problem, 2: indicating slight problems, 3: indicating moderate problems, 4: indicating severe problems, 5: indicating extreme problems), and a separate VAS.

Patients' responses to the EQ-5D-5L will be combined into a unique health state using a 5-digit code with one digit from each of the 5 dimensions representing the level of severity. These EQ-5D-5L states will be converted into a single preference-weighted health utility index score by applying country-specific weights (if available) or US weights (if not available). [3]

No imputation will be performed for missing items, and in case of missing items no index score will be calculated.

A summary table will show descriptive statistics (n, mean, median, SD, minimum and maximum) of the index score values and for the VAS values for baseline and the post-baseline time points, as well as changes from baseline, by cirrhosis status and treatment regimen.

Assessment of work productivity and activity impairment – WPAI Hep C V2.0

The WPAI questionnaire will be used to measure work absenteeism, work presenteeism, and daily activity impairment. The WPAI Hep C V2.0 is the HCV specific questionnaire that will be used in this study. Respondents are asked about time missed from work and time while at work during which productivity was impaired in the past seven days. Results of WPAI are expressed as a percentage of impairment from 0 to 100, with higher percentages indicating greater impairment and less productivity:

- % Presenteeism – percentage of impairment while working due to health problem
- % Absenteeism – percentage of work time missed due to health problem
- % Total work productivity impairment (TWP) – percentage of overall work impairment due to health problem
- % Total activity impairment (TAI) – percentage of general (non-work) activity impairment due to health problem

The WPAI Hep C v2.0 consists of 6 questions aimed at the following targets:

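### Resource use before and during treatment is shown as raw sums over windows of unequal length, so an unchanged rate reads as a 3-fold (12-week) or 6-fold (24-week) rise

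*SAP*

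**What the plan says.** SAP 4.2.7.2.3 announces the display as follows: "Resource utilization within the four weeks prior to the start of the ABBVIE regimen and until EoT (since baseline) will be displayed". It is produced for the core population by genotype and cirrhosis status, and for the safety population by treatment regimen and cirrhosis status.

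Each count is a plain total, for example "number of outpatient consultations [defined as sum of all visits] - continuous and categorized as 0, 1-3, 4-6, >=7". Hospitalisation periods, hospital days and technical interventions are built the same way, each with one set of cut-points for both periods. Individual interventions and symptoms are ever/never items: "Interventions performed (patient is counted at most once per intervention".

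The data come from Protocol Annex 1. The baseline form asks about "Outpatient consultation(s) in the 4 weeks prior to starting the ABBVIE REGIMEN". The on-treatment and EoT forms instruct: "Please document for each outpatient consultation since last visit the technical interventions performed and the symptoms treated". Protocol 9.4.1.1 adds: "Patients can be enrolled in the PMOS during the first 4 weeks of treatment".

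Determining the regimen's impact on resource use is a secondary objective (Protocol 8.2.2, SAP section 2). Protocol 9.7 contains no analysis of resource use, so SAP 4.2.7.2.3 is the only one in the available text. For EQ-5D-5L, SAP 4.2.7.2.2 summarises values at each time point "as well as changes from baseline, by cirrhosis status and treatment regimen". Nothing comparable is written for resource use. The table layouts are in SAP Part II, which is not available here.

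**The concern.** The first window is 4 weeks long. The second is a treatment course of 12 or 24 weeks (Protocol 9.2.2), less any time not counted at its start. Totals over windows of such different lengths differ even when nothing has changed. A reader looking for the impact named in the objective will compare the two, and the display will suggest that use went up.

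Two features make this harder to correct by eye. The analysis groups in SAP 4.2.1 are not split by treatment duration, so 12- and 24-week courses can share a column. And the SAP does not say when the since-baseline window opens for resource use, although a patient may enrol up to 4 weeks into treatment.

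At stake is the reading of one descriptive secondary objective.

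**Working it through.** The plan gives no ratio or rate on this point, so there is no figure of its own to reproduce.

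**Inputs from the documents.** Pre-treatment window 4 weeks (Annex 1, SAP 4.2.7.2.3). Courses of 12 and 24 weeks (Protocol 9.2.2). Latest enrolment week 4 of treatment (Protocol 9.4.1.1).

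**Summed counts.** At a constant rate, the ratio of expected counts is (T − s)/4, where T is the course length in weeks and s is the week at which counting starts.

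| | 12-week course | 24-week course |
|---|---|---|
| From first dose (s = 0) | 12/4 = 3 | 24/4 = 6 |
| From a week-4 visit (s = 4) | 8/4 = 2 | 20/4 = 5 |

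The true fall that would display as no change is 1 − 4/(T − s):

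- From first dose: 1 − 4/12 = 66.7% and 1 − 4/24 = 83.3%.
- From week 4: 1 − 4/8 = 50% and 1 − 4/20 = 80%.

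A true halving, counted from first dose, therefore displays as 0.5 × 3 = 1.5 times or 0.5 × 6 = 3 times the pre-treatment figure. From week 4 it displays as 1.0 or 2.5 times.

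**Early stopping.** A course stopped at week 8 gives 8/4 = 2 from first dose, or 4/4 = 1 from week 4.

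**Mixed durations.** The documents do not give the share *p* on 24 weeks. The overall column shows 3(1 − p) + 6p from first dose. For an assumed *p* of 5% to 25% that is 3.15 to 3.75. From week 4, 2(1 − p) + 5p gives 2.15 to 2.75.

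**Categories.** Assume 1 consultation per 4 weeks throughout, Poisson distributed. The share of patients with 4 or more consultations is 1.9% over 4 weeks, 35% over 12 weeks and 85% over 24 weeks.

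**Ever/never items.** With probability q per 4-week period and independent periods, the ratio is [1 − (1 − q)^k]/q, with k = 3 or 6 from first dose. For assumed q = 0.02 it is 2.94 (k = 3) and 5.71 (k = 6). For q = 0.50 it is 1.75 and 1.97. These items are inflated too, but less as they become common.

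**After the fix.** Total events divided by total patient-weeks, times 4, gives a ratio of 1.0 at an unchanged rate, for either course and any start, provided events and weeks are counted over the same period.

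**The case against.** The strongest reply is that no comparison is planned. SAP 4.2.7.2.3 specifies no change score, difference or test, both windows are openly labelled, and a total per treatment course is a legitimate measure. This stands, and it limits the harm to how the display is read. It does not remove the harm, because these tables are all the plan offers for an objective about impact.

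A reader might infer that window length cannot be disentangled from impact at all. The documents do not support that. SAP 4.2.8.1 summarises treatment duration for the safety population by regimen and cirrhosis status. The adherence section of SAP 4.2.7.2.1 gives actual against target duration for the core population by genotype and cirrhosis status. These are the strata of the resource-use tables, so a rough group-level rate could be worked out. Splitting by cirrhosis status may also confine much of the mixing of 12- and 24-week courses to the cirrhosis and overall columns.

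A reader might also infer that the first 4 weeks of treatment are lost for late enrollees. That follows only if the window opens at the enrolment visit and the charts are not used to fill the gap. SAP 4.2.2 places baseline at or before study day 1 for HCV RNA and laboratory data, and the Annex 1 baseline form looks back from treatment start. Protocol 9.4.1 draws data from patient charts where available. Since SAP 4.2.2 does not cover resource use, the factors of 2 and 5 remain a conditional lower case.

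The baseline form offers at most 4 consultations, so the top category (7 or more) must be empty before treatment. An empty category is not an error, and nothing here rests on it.

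Finally, the table shells could contain a rate or a window label. That cannot be excluded; the point concerns the SAP text, which defines sums.

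**Conclusion.** The point holds as a minor defect of presentation. Followed as written, the SAP text yields an apparent 3-fold (12 weeks) or 6-fold (24 weeks) rise at an unchanged rate, and it can reverse the apparent direction of a real fall smaller than 67% or 83%. These figures assume a completed course, counting from first dose, and two separate windows, which the separate Annex 1 forms favour. Early stopping lowers them. If counting starts at a week-4 enrolment visit without earlier chart data, they become 2 and 5. The figures for mixed durations, categories and ever/never items rest on assumed inputs and are illustrations only.

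No planned test or estimate of change is biased, because none is specified. SVR12 and safety conclusions are unaffected.

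**What to change.** In SAP 4.2.7.2.3:

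1. Define the start of the since-baseline window for resource use (for example, first dose). State how the weeks between first dose and a later enrolment visit are counted, in both numerator and denominator.
2. For each count and for hospital days, add the pooled rate per 4 weeks for both windows (total events / total patient-weeks covered × 4), with 12- and 24-week courses separate in the overall column.
3. If a within-patient rate difference is also shown, report the median and range and state a minimum on-treatment time covered. Individual rates are unstable after short exposure: 2 consultations in 1 week become 2/1 × 4 = 8 per 4 weeks.
4. Keep the raw counts, labelled as totals per course.
5. Label ever/never items with their window length and as not comparable between windows.

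The cost is one derived variable (weeks covered, from visit and treatment dates) and a few extra rows; no new data, test or count model is needed. Splitting every column by duration is not worthwhile. Even if all 50 to 55 patients entered the core population, its 6 disjoint cells (cirrhosis status by G1a, G1b, G4) would average 50/6 = 8.3 to 55/6 = 9.2 patients.

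The comparison stays uncontrolled and descriptive, and the 4 weeks before treatment may not reflect a steady rate. It is also imprecise. With 50 to 55 patients all on 12 weeks, an assumed 1 consultation per 4 weeks in both windows, Poisson variance and independent windows, the 95% half-width of the difference is 1.96 × √[(1 + 4/12)/n]. That is 0.31 (n = 55) to 0.32 (n = 50) per 4 weeks, or 0.53 to 0.55 if the variance is three times as large.
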